10.2.2.6.4 Biomarkers

Descriptive statistics will be provided for biomarkers and treatments will be compared using analysis of variance (ANOVA), or non-parametric method when appropriate, of specific genes (e.g., T-cell receptors) and/or gene-networks (e.g., signaling of immune cells) and gene modules (e.g., sets of genes [typically 100-200]) that are up- or down-regulated in concert in certain conditions or disease states (e.g., infection, autoimmunity, etc.) will be performed. Data will be used to compare the baseline with responses post-treatment. Additionally, joint models of overall survival and longitudinal biomarkers may be explored.

10.2.2.6.5 Tumor Growth Rate, Progression Arrest Rate, Clinical Benefit Rate, and Quality of Life

Tumor growth rate and PAR will be explored between treatment arms. Additionally, the relationship between TGR and OS, and PAR and OS, may be explored.

Clinical benefit rate will be explored using methods similar to that described for ORR.

Quality of life as a composite endpoint (including but not limited to the following: while on study, the incidence of hospitalization, transfusions, and laboratory markers [eg. absolute neutrophil count, hemoglobin, and platelets]) will be explored.

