	
Exploratory comparisons of the OS, PFS, and DOR between treatment arms will be based on stratified log-rank tests. ORR will be compared between treatment groups using a stratified logistic regression model. Weighted log-rank tests will be explored if delayed treatment effect is observed; TGR, PAR, CBR, and quality of life will be evaluated for each group.
 
Safety Descriptive statistics will be performed for all safety information including AEs, SAEs, laboratory findings and discontinuations of patients at all data collection timepoints. No formal statistical hypothesis will be tested.
 
Immunogenicity Descriptive statistics will be performed comparing the baseline and treatment administration peripheral blood NY-ESO-1-responsive T cells between the 2 treatment arms. Analyses will be performed to determine if there are any statistically significant changes from baseline values. Changes from baseline in serial anti-NY-ESO-1 antibodies will be expressed as geometric mean titers.
 
Biomarkers Descriptive statistics will be provided for biomarkers and treatments will be compared using ANOVA, or non-parametric method when appropriate, of specific genes and/or analysis of gene-networks (e.g., signaling of immune cells) and gene modules (e.g., sets of genes [typically 100-200]) that are up- or down-regulated in concert in certain conditions or disease states (e.g., infection, autoimmunity, etc.) will be performed. Data will be used to compare the baseline with responses post-treatment. Additionally, joint models of overall survival and longitudinal biomarker data may be explored.

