4.2.3 Exploratory Endpoint

The exploratory endpoints are the following:

- TGR
- PAR
- To compare OS and PFS between treatment arms
- ORR as assessed by RECIST (v1.1) modified to use irRC
- DOR
- CBR
- Immune responses as measured by changes from baseline in anti-NY-ESO-1 immunity
- Biomarkers
- Quality of life

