Peripheral blood will be collected for immunogenicity assays at baseline, then on Days 42, 70, and 98 (\pm 2 weeks). Tissue biopsies will be taken in each treatment group from consenting subjects before treatment and on Day 42, on Day 98 (\pm 2 weeks), at 6 months or longer (for patients with treatment response), and at the time of progression to assess immune cell invasion, including changes in PD-L1, CD4, CD8/Ki-67 and/or CD3/perforin expression. If a patient undergoes a tumor biopsy at any time after disease progression, investigators are strongly encouraged to provide biopsy tissue to the sponsor for immune response and tumor changes analysis.

Imaging will be performed approximately every 6 weeks for 12 months, then every 12 weeks for tumor staging until progression. Tumor responses will be assessed at the sites by evaluating tumor images/scans using RECIST modified to use irRC-specified confirmation and unidimensional tumor measurements. Adjudication will be performed by blinded independent central review (BICR) following the same rules. The irRC modification requires a confirmation of CR/PR/progressive disease (PD) at least 4 weeks later with imaging; once confirmed, the date of progression is defined as the first date that the total tumor burden was shown to have increased by at least 20% compared with the nadir.

Patients will be followed until confirmed radiographic disease progression to determine ORR and PFS. In addition, OS status will be followed up until the end of the trial. If the patient dies, the date of death will be documented by the local physician and/or registries.

All SAEs, DLTs, and MEOIs deemed potentially related to the study agents will be reviewed by the Sponsor and an independent Data Monitoring Committee (DMC).

Following completion of CMB305 dosing, patients will continue with clinical assessment and imaging approximately every 6 weeks until disease progression, as defined by RECIST (v1.1) modified to use irRC. The expected duration of a patient's participation in the trial is up to 2.1 years, including Screening, Treatment Phase, Booster Phase (for patients in the combined treatment arm), and Maintenance Phase (with follow-up visits until disease progression). Patients will then enter the Survival Follow-up Phase and their physicians will be contacted every 3 months by telephone to assess OS.

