9.3.2 Immune Response

The following exploratory immune monitoring will be conducted:

- Cellular immunogenicity as measured by changes from baseline and over the course of the trial period in peripheral blood levels of T cells, T-cell effector and memory populations, and T-cell associated cytokine production.
- Humoral immunogenicity as measured by changes from baseline and over the course of the trial period with anti-NY-ESO-1 antibodies or TAAs.
- Evaluation of dosing response by RNA profiling of PBMCs as measured by the changes from baseline.

Details for sample handling and assay performance will be provided in the Immune Monitoring Manual.

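### The exploratory biomarker comparison between arms names no baseline or disease-type adjustment and does not say how serial samples are handled: valid readings exist, but they give away power

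*Protocol*

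**What the plan says.** Protocol 10.2.2.6.4 (Biomarkers) sits under the exploratory analyses. For specific genes, gene networks and gene modules it states that "treatments will be compared using analysis of variance (ANOVA), or non-parametric method when appropriate", and then "Data will be used to compare the baseline with responses post-treatment". It adds that "joint models of overall survival and longitudinal biomarkers may be explored". The synopsis repeats the between-arm method: "treatments will be compared using ANOVA, or non-parametric method when appropriate". No response variable, visit, model term or paired method is given in either place.

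Sampling is repeated within patients. Protocol 5.1 states that "Peripheral blood will be collected for immunogenicity assays at baseline, then on Days 42, 70, and 98", and that "Tissue biopsies will be taken in each treatment group from consenting subjects before treatment and on Day 42". Further biopsies follow on Day 98, at 6 months or longer in responders, and at progression.

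Two other passages bear on the response scale. Protocol 9.3.2 lists "Evaluation of dosing response by RNA profiling of PBMCs as measured by the changes from baseline", and Protocol 4.2.3 lists "Immune responses as measured by changes from baseline in anti-NY-ESO-1 immunity".

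Protocol 10.2 defers analysis details to the SAP. SAP 7.6.2.2 covers pre- and post-dosing summaries of antibody and T-cell status, associations with PFS and OS, and stepwise Cox regression. It mentions no ANOVA, mixed model, paired test or baseline covariate. SAP section 8 lets the SAP prevail where the two documents differ, but on this comparison it offers nothing in place of the protocol method.

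**The concern.** The patient is the unit of randomisation, and each patient is meant to give a baseline sample and several later ones. A comparison of arms on such data should say three things: which value is analysed, whether the patient's own baseline is used, and how several samples from one patient enter the model. Neither document does.

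Randomisation is stratified by disease type (Protocol 7.2.1). The plan carries that factor into the between-arm analyses of PFS, OS and ORR (Protocol 10.2.2.6.1 and 10.2.2.6.2; SAP 7.6.1.1 and 7.6.3.2), but not into this one.

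Two things are at stake. With at most about 40 patients per arm, leaving out a baseline covariate that has already been collected gives away precision. And an open choice of response scale and visit lets the analysis be settled after the data are seen.

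**Working it through.** The documents state no power or error rate for the biomarker analysis, so there is no figure of theirs to reproduce. The check compares the single-visit analyses that the wording allows with a baseline-adjusted analysis.

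**Inputs**
- Patients per arm: n = 40 (Protocol 10.3.1, approximate).
- Two-sided 5% level (SAP 7.9).
- True difference between arms: 0.5 SD of the post-treatment value. This is an assumption; the documents give none.
- Within-patient correlation ρ between baseline and post-treatment value: 0.3, 0.5 and 0.7, also assumed.

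**Formulas.** With equal variances at both times, the variance of the outcome relative to the post-treatment value alone is:
- post-treatment value only: 1
- change from baseline: 2(1 − ρ)
- ANCOVA on baseline: 1 − ρ²

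The standardised effect is d = 0.5 / √(relative variance). Power comes from the two-sample t test with non-centrality d·√(n/2).

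**Results, 40 per arm**

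| ρ | Post only: variance, d, power | Change: variance, d, power | ANCOVA: variance, d, power |
|---|---|---|---|
| 0.3 | 1.00, 0.500, 60% | 1.40, 0.423, 46% | 0.91, 0.524, 64% |
| 0.5 | 1.00, 0.500, 60% | 1.00, 0.500, 60% | 0.75, 0.577, 72% |
| 0.7 | 1.00, 0.500, 60% | 0.60, 0.645, 81% | 0.51, 0.700, 87% |

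A normal approximation gives values about one point higher.

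ANCOVA gains against both readings at every ρ shown. Against post-only ANOVA the variance ratio is 1 − ρ², so 40 per arm does the work of 40/0.91 = 44, 40/0.75 = 53 or 40/0.51 = 78 per arm. Against the change score the ratio is (1 − ρ²) / [2(1 − ρ)] = (1 + ρ)/2, that is 0.65, 0.75 or 0.85, so 40 does the work of 62, 53 or 47.

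**Fewer evaluable patients.** Forty is a ceiling. Patients may decline the Day 98 biopsy (Protocol 5.1), and blood for cellular immunity is taken only at sites trained in PBMC isolation (Protocol Tables 1 and 2, footnotes). With an assumed 30 per arm the same formulas give 48% for post-only, 36, 48 and 69% for change, and 51, 59 and 76% for ANCOVA.

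**Validity of the single-visit readings.** Each uses one value per patient, so the observations are independent. In a simulation with no true effect (20,000 trials per setting, 40 per arm), rejection rates were 0.048 to 0.052 for the change score and 0.048 to 0.054 for the post-treatment value alone. Both hold the 5% level.

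**The case against.** **A reader might infer that the named ANOVA must either ignore the pairing or treat serial samples as independent.** The documents do not support that. They leave the model unstated; they do not state a wrong one. Change from baseline at one visit uses the pairing, fits the scale set in Protocol 9.3.2 and 4.2.3, and keeps its level. A repeated-measures ANOVA or a signed-rank test would fit the wording too.

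**A reader might also attach an inflated false-positive rate to the plan.** If m correlated visits per patient were pooled as independent, the actual error would be 2[1 − Φ(1.96/√(1 + (m − 1)ρ))]. At ρ = 0.5 that is about 11% for m = 2 and 17% for m = 3. The arithmetic is right, but no passage says visits will be pooled in this way. The figures show why the handling of serial samples should be written down; they are not a property of the plan.

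**The stakes can be overstated.** Immune response and tissue change is a secondary endpoint, but Protocol 10.2.2.4.2 only summarises it by arm. The ANOVA belongs to the exploratory biomarker endpoint. The blood schedule in Protocol 5.1 is for immunogenicity assays, which have their own section (10.2.2.6.3). The biopsies, and the RNA profiling of blood cells, keep the repeated-sampling point alive for biomarkers.

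**It is also arguable that the SAP retires the ANOVA by not mentioning it.** If so, no between-arm biomarker method is specified at all, and the request to state one still holds.

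What stands on the other side is that choosing ANCOVA over a single-visit change score is a gain in efficiency, not the correction of an error.

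**Conclusion.** The point holds as a gap in specification with an avoidable loss of power. The between-arm biomarker comparison names neither a baseline covariate nor the stratification factor, and neither document says how serial samples from one patient are handled. Under the assumptions above, baseline adjustment at 40 per arm adds about 4, 12 or 27 points of power over post-only ANOVA, and about 18, 12 or 6 points over a change score, at ρ of 0.3, 0.5 or 0.7. These sizes depend on an effect and a correlation that the documents do not give. That ANCOVA has the lower variance does not depend on the effect size; it follows from the formulas for any ρ strictly between 0 and 1. No figure is offered for disease type, because nothing in the documents says how strongly it predicts the biomarkers.

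Severity is minor. Protocol 10.4 calls all p-values nominal, SAP 7.9 treats between-arm comparisons as exploratory and the p-values as descriptive, and the futility rule in Protocol 10.3 uses only the 6-month progression-free rate.

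**What to change.** In Protocol 10.2.2.6.4 and the synopsis, replace the ANOVA wording. In SAP 7.6.2.2, add the model:

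- **One visit:** ANCOVA of the post-treatment value at a named visit on arm, baseline value and disease type, with the biomarker log-transformed or rank-transformed where it is skewed.
- **Several visits together:** a mixed model with arm, visit, arm-by-visit interaction, baseline value, disease type and a patient random effect. Restrict it to visits scheduled for all patients, because the 6-month-or-longer and progression biopsies are triggered by outcome.
- **Within arm, baseline to post-treatment:** paired tests (paired t or Wilcoxon signed-rank).

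The cost is wording in two documents and standard code; no new data are needed. The downside is that patients without a baseline sample drop out of the ANCOVA, or need a mixed model that treats baseline as an outcome with a common mean across arms. If the sponsor does not wish to amend the protocol for an exploratory analysis, SAP section 8 allows the SAP to carry the change alone.

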10.3 Interim Analysis

An exploratory analysis of the PFR at 6 months after treatment initiation will be used as a non-binding futility analysis for each treatment arm. Upon obtaining the progression status after 6 months on study from the first 36 (18 per arm) and subsequently from all enrolled patients, interim analyses will be performed and presented to the DMC, which will include estimates of PFS and assessment of PFR. Based on the assumptions in Section 10.3.1, futility guidelines at Stage 1 will be based on 18 patients and will require at least 6 patients to be progression free to

continue on to Stage 2. With an additional 22 patients at the end of Stage 2, at least 14 of the total of 40 patients should be progression free at 6 months after initial dosing to recommend further study in this setting. No formal interim analysis will be performed for efficacy. For the purposes of safety monitoring, key safety analysis will also be performed quarterly. The DMC will evaluate the available data and make necessary recommendations to the study. Details will be outlined in the DMC charter.

A final analysis will be conducted when at least 72 deaths have been observed, or sooner if the Sponsor so decides.

10.3.1 Sample Size

The median PFS for first-line chemotherapy for patients with metastatic synovial sarcoma has been reported to be 2.5 to 8.3 months; 34 PFS with atezolizumab in the post-chemotherapy setting is unknown. Thus, no power calculations based on comparisons of PFS were made. However, based on an unacceptable and desirable median PFS of 3 months and 5.2 months, respectively, corresponding PFRs at 6 months were derived. With an unacceptable PFR of 25% and an acceptable PFR of 45% at 6 months, a Simon 2-stage design will be used to examine the PFR in 40 patients in each arm ($\alpha=0.1$, $\beta=0.15$). For this study, two groups of approximately 40 patients each (approximately 80 patients total) will be dosed with CMB305 with atezolizumab or with atezolizumab alone to assess the quartiles (25%, 50%, and 75%) of PFS with 95% confidence intervals (CIs) and the PFR at 6 months. If favorable results are observed, the study may be expanded to improve the estimates of PFS.

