#### IMDZ-C232

Abbreviations: AE = adverse event, CT = computed tomography; ECG = electrocardiogram; ECOG = Eastern Cooperative Oncology Group; HepB = hepatitis B; HepC = hepatitis C; HIPAA = Human insurance Portability and Accountability Act; HIV = Human immunodeficiency Virus; meds = medications; mos = months; PBMC = peripheral blood mononuclear cells; SAE = serious adverse event.

- a. A window of ±3 days is permitted for Visits 3 through 12. Follow-up phase visits (Visits 13+) will be permitted a window of ±4 days, Tumor assessments will be permitted a window of ±1 week.
- b. Patients will be followed with visits every 3 weeks (±4 days) for 2 years (from Day 0) for until progression. Tumor size will be assessed every 6 weeks for the first year, then every 12 weeks until progression. Patients will then have no further staging procedures. Tumor biopsies will be obtained at 6 months or longer for patients with treatment response. Tumor biopsies will also be obtained at time of progression.
- c. Informed consent and HIPAA authorization must be signed before any screening study-related procedures are initiated. Three informed consents will be used: one to screen tumor sample for NY-ESO-1, one to engage in the study protocol, and an agreement to continue in the study and obtain peripheral blood samples and biopsies if the patient meets the criteria for progressive disease but wishes to remain on study.
- d. Documentation of NY-ESO-1 expression in prior tumor samples may have been collected from any procedure performed before baseline activities. There is no time limit for use of the results from the IMDZ-approved central lab.
- e. Vital sign measurements include temperature, pulse, respiratory rate, and resting systolic and diastolic blood pressure. On the day of each dosing, vital signs will be obtained pre-dosing and 30 minutes after dosing. For the first atezolizumab infusion, the patient's vital signs (HR, respiratory rate, BP, and temperature) should be measured within 15 minutes of the infusion, during the 60-minute infusion (every 15 [± 5] minutes), and 30 minutes after the infusion. For subsequent infusions, vital signs do not need to be obtained during the infusion if the prior infusion was tolerated without symptoms.
- f. Once the baseline physical exam has been conducted, a simple symptom-directed physical exam should be performed for all subsequent visits. Height and weight will be collected at Day 0 only.

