- g. Imaging will be performed by CT scan as defined by RECIST/irRC at screening and every 6 weeks after first study injection for the first year, then every 12 weeks for tumor staging until disease progression and includes a confirmatory scan performed at least 4 weeks later. Magnetic Resonance Imaging (MRI), bone scans, or PET/CT at baseline or subsequent visits will be performed only if clinically indicated.
- h. An HIV screening test will be repeated on Day 168 to determine if seroconversion has occurred following LV305 injections. If positive, further testing can demonstrate that the normal complement of HIV proteins is not present (unless the patient has developed a true HIV infection).
- i. Blood for immunogenicity will be collected at clinical sites that are trained in peripheral blood mononuclear cells (PBMC) isolation. Baseline samples will be drawn twice to ensure a good yield. At least 55 mL should be collected in 8 Cell Preparation Tubes (CPT)TM tubes for T-cell response assays. See the Lab Manual for processing details.
- j. Initial safety labs are to be performed within 4 days before treatment initiation. On treatment days during the study dosing period, the hematology and clinical chemistry laboratories must also be performed and reviewed before dosing and may be performed up to 48 hours prior to the planned dosing.
- k. Thyroid function tests (triiodothyronine [T3], thyroxine [T4], and thyroid stimulating hormone [TSH]) should be taken at initial screening and at least every 3 months while being treated with atezolizumab. As thyroid disorders could occur at any time as a result of atezolizumab treatment, patients should be monitored for changes in thyroid function for clinical signs and symptoms of thyroid disorders (at the start of treatment, periodically during treatment, and as indicated based on clinical evaluation).
- Urine pregnancy test must be performed for women of childbearing potential within 72 hours before study drug administration and negative before study drug administration, including during the follow-up period if patients are still receiving booster doses of G305 and/or atezolizumab. Serum pregnancy test may be performed if the site's standard operating procedures allow.
- m. Booster doses of G305 will be given 6 weeks following the Day 84 dose and every 6 weeks thereafter for 1 year (from Day 0) or until disease progression at the staging visits.

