# **4 SAMPLE SIZE DETERMINATION**

Sample size was calculated using a Simon 2-stage design, assuming an unacceptable progression-free survival rate (PFR) of 25% and an acceptable PFR of 45% at 6 months, corresponding to an unacceptable and desirable median PFS of 3 months and 5.2 months, respectively and an exponential survival distribution, 40 patients in each arm (alpha=0.1, beta=0.15) were required. For this study, two groups of up to 40 patients each (up to 80 patients) were to be dosed with CMB305 with atezolizumab or with atezolizumab alone to assess PFS at 6 months and median of PFS with 95% CIs. If favorable results are observed, the study may be expanded to improve the estimates of PFS.

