# 7.6.2 Analysis of Secondary Efficacy Variables

# 7.6.2.1 PFR at 6 Months

PFR at 6 months using Kaplan-Meier method, with 95% and 80% confidence intervals (CIs) by treatment arm will be presented. If the Lower Confidence Limit of the 80% CI is greater than the assumed unaccepted PFR rate of 25%, it would serve as a signal that PFR at 6 months is higher than 25%.

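### The 25%/45% PFRs are derived at exactly 6.0 months, where no scan falls; if 25% is the underlying rate, the go rule's false-positive rate is up to about 16–20% with on-time scans

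*Protocol*

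**What the plan says.** Protocol 10.3.1 explains where the two rates come from: "based on an unacceptable and desirable median PFS of 3 months and 5.2 months, respectively, corresponding PFRs at 6 months were derived". It continues: "With an unacceptable PFR of 25% and an acceptable PFR of 45% at 6 months, a Simon 2-stage design will be used". SAP Section 4 adds the model: "corresponding to an unacceptable and desirable median PFS of 3 months and 5.2 months, respectively and an exponential survival distribution". On that basis "40 patients in each arm (alpha=0.1, beta=0.15) were required".

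Protocol 10.3 gives the rule. At least 6 of the first 18 patients in an arm must be progression-free at 6 months to continue, and at least 14 of 40 to recommend further study. The look is exploratory and non-binding.

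The SAP estimates PFR at 6 months by Kaplan-Meier (5.1.2.1). It does not repeat the 14 of 40 bar. Instead it takes as a signal (7.6.2.1): "If the Lower Confidence Limit of the 80% CI is greater than the assumed unaccepted PFR rate of 25" per cent. SAP Section 8 says the SAP prevails over the protocol.

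On imaging, SAP Table 1 footnote g has CT "every 6 weeks after first study injection for the first year", and footnote a says "Tumor assessments will be permitted a window of ±1 week". Under Protocol 10.2.2.4.1 and SAP 5.1.1.1, confirmed progression is dated at the first scan that showed the 20% increase. SAP Table 3 dates deaths and symptomatic deterioration on their own days.

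**The concern.** Six months is Day 182.6, or Week 26.1. The scans either side are Week 24 (Day 161–175 with the window) and Week 30 (Day 203–217), so neither window contains the landmark. Radiological progression that occurs after the Week 24 scan but before Day 182.6 is found and dated near Week 30. At the 6-month landmark that patient still counts as progression-free.

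The Kaplan-Meier curve is therefore close to flat from Week 24 to 6 months, and its 6-month value is essentially the Week 24 value. The comparator, 25%, was derived 2.1 weeks later on a smooth curve. If the two are on different footings, a regimen with the unacceptable 3-month median passes more often than the stated alpha of 0.1. The rule informs whether to recommend further study, and the plan allows expansion if results are favourable. This arises on the 6-weekly schedule itself, separately from the 6-to-9-week interval mentioned in Protocol 5.7 and 9.3.1.

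**Working it through.** **Inputs.** Medians 3 and 5.2 months, exponential (Protocol 10.3.1, SAP 4); 30.4375 days per month (SAP 5.1.1.1); rule of at least 6/18 then at least 14/40 (Protocol 10.3); 80% two-sided limit against 25% (SAP 7.6.2.1); scans every 42 days from first dose, ±7 days.

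**1. The plan's own figures.** S(6) = 0.5^(6/3) = 25.0% and 0.5^(6/5.2) = 44.9%, matching 25% and 45%. The pass probability is the sum over x = 6 to 18 of P[Bin(18,p) = x] × P[Bin(22,p) ≥ 14 − x]. With Stage 1 ignored it is P[Bin(40,p) ≥ 14].

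| True rate | Stage 1 followed | Stage 1 ignored |
|---|---|---|
| 25% | 0.080 | 0.103 |
| 45% | 0.856 | 0.925 |

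The stated design reproduces; the 0.103 exceeds 0.1 only trivially.

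**2. Rate the estimate targets.** 6 × 30.4375 = 182.6 days. The last scheduled scan before that is Day 168. With all events found by on-time scans:
- 3-month median: 0.25^(168/182.6) = 0.25^0.920 = 27.9%.
- 5.2-month median: 0.5^((168/30.4375)/5.2) = 47.9%.

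Averaging the 3-month-median rate over Day 161–175 also gives 27.9%.

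**3. The 14 of 40 rule at those rates.**

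| True median | Rate at Week 24 | Stage 1 followed | Stage 1 ignored |
|---|---|---|---|
| 3 months | 27.9% | 0.161 | 0.204 |
| 5.2 months | 47.9% | 0.914 | 0.965 |

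**4. The SAP rule.** With complete follow-up, the 80% lower limit is 23.0% (linear) or 23.3% (log-log) at 13/40, and 25.3% or 25.5% at 14/40. It first clears 25% at 14/40, so it carries the same single-look figures: 0.103 at a rate of 25% and 0.204 at 27.9%. Simulating it with ±1-week scan jitter and 0–30% of events dated exactly gives about 0.17–0.20.

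**5. Sensitivity at a 3-month median (assumed scenarios).** Where a share f of events is dated exactly, rate = 25% + (1 − f) × (27.9% − 25%).

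| Scenario | Rate | Stage 1 followed | Stage 1 ignored |
|---|---|---|---|
| 30% of events dated exactly | 27.1% | 0.133 | 0.169 |
| 50% of events dated exactly | 26.5% | 0.116 | 0.148 |
| All scans at Day 161 | 29.5% | 0.217 | 0.271 |
| All scans at Day 175 | 26.5% | 0.117 | 0.149 |
| Day 168 scan, randomised 4 days before dosing | 27.1% | 0.135 | 0.171 |
| Day 175 scan, 4-day gap, plus 1 day | 25.5% | 0.092 | 0.118 |
| Status read at the Week 30 scan instead | 20.3% | 0.017 | 0.022 |

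In the last row, power at a 5.2-month median is 0.69 or 0.78.

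**The case against.** A reader might infer that the sample-size arithmetic is wrong, or that the go rule has a fixed false-positive rate of 16–20%. The documents support neither. At a PFR of 25% the design meets its stated alpha and beta, and the inflation is conditional.

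- **Scale of the 25%.** PFS in this plan is defined by documented progression. If the 3-month median and the 25% were meant on that scale, 25% is already the rate the estimate targets, and 8.0% or 10.3% stands. This is the strongest point. Against it, the only derivation given is a smooth exponential read at 6.0 months, which does not describe a curve that steps at scans. The scale is left unstated.
- **Exactly dated events.** Deaths and symptomatic deterioration count on their own dates, so not all events after Week 24 are missed. This lowers the figure but does not remove the effect.
- **Clock and window.** PFS runs from randomisation, up to 4 days before dosing, while scans run from first dose. Across the clock and window scenarios, the false-positive rate runs from about 0.09 to 0.27.
- **Direction.** Protocol 10.3 asks for status after 6 months without a reading rule. Reading it at the Week 30 scan would make the rule strict instead. The SAP's Kaplan-Meier estimate by event date, which prevails, points to Week 24.
- **Power.** It rises too, so the operating point shifts; the design does not fail.
- **Consequence.** The rule is exploratory and non-binding, PFR is secondary, and p-values are nominal. A must-fix label would be too strong.

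**Conclusion.** The point holds in conditional form. The null and target rates are set at Day 182.6, while the SAP's estimate is in effect read at Week 24, and the plan does not reconcile the two or say on which scale 25% applies.

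If 25% is the underlying rate for a 3-month median, the expected estimate is about 28%. With on-time scans, the false-positive rate is then up to about 16% with Stage 1 followed or 20% with it ignored, falling to about 13% or 17% if 30% of events are dated exactly. If 25% is a documented, scan-dated rate, the stated alpha is right. The calculations assume exponential progression times and complete follow-up. Severity is minor to moderate.

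**What to change.** In Protocol 10.3 and 10.3.1 and SAP 4, 5.1.2.1 and 7.6.2.1, do one of the following:

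1. Tie PFR to the Week 24 scan and its window, derive the null and target rates at that same time (about 28% and 48%), and compare the 80% lower limit with that null.
2. Keep 25% and 14 of 40, and state that the false-positive rate at a 3-month median is up to about 16% (Stage 1 followed) or 20% (ignored).

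In either case, state whether the rates are underlying or scan-dated.

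A higher bar should not be imposed on this evidence. If the bar is revisited, show both candidates at 27.9% and 47.9% (Stage 1 followed / ignored):

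| Bar | False-positive rate | Power |
|---|---|---|
| 15/40 | 0.104 / 0.122 | 0.89 / 0.93 |
| 16/40 | 0.061 / 0.067 | 0.85 / 0.88 |

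If 25% and 45% are scan-dated rates after all, 16/40 would cut power to about 0.75 / 0.79.

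The cost is wording and a slightly less favourable stated figure or threshold. No patients or scans are added.
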